#### **8.2.4.4. Overall survival**

Percentages of deaths and their causes of death will be summarized as per Section 8.1.2.

Overall survival (OS) will be analyzed using the entire analysis set and also by HSCT performed or not performed after the start of this drug, as per Section 8.1.4. Those who included in the analysis are patients in the EAS who finished the survey (Patients who are recorded as discontinued in the "Record of continued/discontinued survey [treatment period]" in the case report form or patients for whom "Record of continued/discontinued survey [follow-up period]" in case report form is filled in. The latter means the survey is discontinued and completed for the patient.). The time points for rate estimation will be at Months 3, 6, 9, and 12 for the entire analysis set and patients who did not undergo HSCT, and at Months 3, 6, 9, 12, 18, and 24 for patients who underwent HSCT. Results of the analysis for the entire analysis set should be interpreted with caution, because the planned observation period for this survey differs for patients who did and did not undergo HSCT after the start of this drug (see Section 2.1).

The OS after the final dose of this drug in patients who underwent HSCT will also be analyzed in the same manner. Those who included in the analysis are patients in the EAS who underwent HSCT after the start of this drug and finished the survey (Patients who are recorded as discontinued in the "Record of continued/discontinued survey [treatment period]" in the case report form or patients for whom "Record of

continued/discontinued survey [follow-up period]" in case report form is filled in. The latter means the survey is discontinued and completed for the patient.).

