- White blood cell count immediately before the start of this drug [ $\leq 4000/\text{mm}^3$ ,  $\geq 4000/\text{mm}^3$ , not performed]
- Neutrophil count immediately before the start of this drug [ $\leq 2000/\text{mm}^3$ ,  $\geq 2000/\text{mm}^3$ , not performed]
- Platelet count immediately before the start of this drug [ $< 10 \times 10^4/\mu\text{L}$ ,  $\geq 10 \times 10^4/\mu\text{L}$ , not performed]
- Peripheral blast count immediately before the start of this drug [ $\leq 1000/\mu\text{L}$ ,  $> 1000/\mu\text{L}$ , not performed]
- Myeloblast count immediately before the start of this drug [ $\leq 50\%$ ,  $> 50\%$ , not performed]
- Salvage line of the induction treatment with this drug [Initial induction, 1st, 2nd, 3rd or later]
- HSCT before the start of this drug [not performed, performed]

Subgroup analyses of safety will be performed also for the following factors:

- HSCT after the start of this drug [not performed, performed]
- Type of the first HSCT after the start of this drug [autologous transplant, allogeneic hematopoietic stem cell transplant with myeloablative conditioning, allogeneic hematopoietic stem cell transplant with nonmyeloablative conditioning, unknown]
- Donor of the first HSCT after the start of this drug [alternative donor, matched related donor]
- Conditioning with alkylating agent for the first HSCT after the start of this drug [ $\leq 1$  agent (including no conditioning),  $\geq 2$  agents]
- Conditioning with busulfan for the first HSCT after the start of this drug [not performed (including no conditioning), performed]
- ECOG PS before conditioning for the first HSCT after the start of this drug [0, 1,  $\geq 2$ , not performed]
- AST and ALT levels before conditioning for the first HSCT after the start of this drug [ $\leq 1.5 \times$  the institutional upper limit of normal range (IULN), either  $> 1.5 \times$  IULN, not performed]
- $\gamma$ -GTP level before conditioning for the first HSCT after the start of this drug [ $\leq 50$  IU/L,  $> 50$  IU/L, not performed]

- Total bilirubin level before conditioning for the first HSCT after the start of this drug [≤ institutional upper limit of normal range (IULN), > IULN, not performed]
- Hemoglobin level before conditioning for the first HSCT after the start of this drug [< 10 g/dL, ≥ 10 g/dL, not performed]
- Platelet count before conditioning for the first HSCT after the start of this drug [< 10 × 10^4/µL, ≥ 10 × 10^4/µL, not performed]

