- Peripheral blast count immediately before the start of this drug [ $\leq 1000/\mu\text{L}$ ,  $> 1000/\mu\text{L}$ , not performed]
- Myeloblast count immediately before the start of this drug [ $\leq 50\%$ ,  $> 50\%$ , not performed]
- Salvage line of the induction treatment with this drug [Initial induction, 1st, 2nd, 3rd or later]
- HSCT before the start of this drug [not performed, performed]
- Pregnancy [absent, present] \* Pregnancy during the treatment period. Limited to cases in which information on pregnancy is collected

Subgroup analyses of overall survival (OS) will be performed for the following patient characteristics and other factors:

- Age [ $< 15$  years,  $\geq 15$  to  $< 65$  years,  $\geq 65$  years]
- Age [ $< 18$  years,  $\geq 18$  to  $< 55$  years,  $\geq 55$  years]
- Age [ $< 15$  years,  $\geq 15$  to  $< 40$  years,  $\geq 40$  years]
- Disease name [Relapsed CD22+ acute lymphocytic leukemia (ALL), refractory CD22+ ALL]
- Chromosome karyotype [normal, t (4;11), unknown]
- Chromosome karyotype [Philadelphia chromosome positive, negative, unknown]\* Philadelphia chromosome is considered positive if the chromosome karyotype is t(9;22).
- Hemoglobin level immediately before the start of this drug [ $< 10\text{ g/dL}$ ,  $\geq 10\text{ g/dL}$ , not performed]
- Platelet count immediately before the start of this drug [ $< 10 \times 10^4/\mu\text{L}$ ,  $\geq 10 \times 10^4/\mu\text{L}$ , not performed]
- Peripheral blast count immediately before the start of this drug [ $\leq 1000/\mu\text{L}$ ,  $> 1000/\mu\text{L}$ , not performed]
- Myeloblast count immediately before the start of this drug [ $\leq 50\%$ ,  $> 50\%$ , not performed]
- Salvage line of the induction treatment with this drug [Initial induction, 1st, 2nd, 3rd or later]
- HSCT before the start of this drug [not performed, performed]
- Pregnancy [absent, present] \* Pregnancy during the treatment period. Limited to cases in which information on pregnancy is collected
- Best overall response [CR or CRi, progression or relapse, indeterminate or other, not performed]
- Best overall response [CR, CRi]\* "Progression", "relapse", "indeterminate/other" and "not performed" are excluded.
- MRD [negativity achieved, negativity not achieved, test not performed] \* Irrespective of the result of best overall response.

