#### 6.2. Effectiveness Endpoints

- Hematologic response. This is assessed as one of the following categories based on the best overall hematologic response: CR, CRi, progressive disease (PD), relapse, indeterminate, other, assessment not performed. "Other" corresponds to the cases where the clinical assessment of hematologic response was performed but the result did not fall into any of the categories described in the case report form, while "assessment not performed" corresponds to the cases where the clinical assessment was not performed.
- MRD. This is assessed as one of the following categories based on the MRD status: negativity achieved, negativity not achieved, unknown, test not performed.
- Overall survival:
  - Overall survival: Defined as the months from the start of this drug to all-cause death.
  - Event: Death
  - Censoring: The patient is confirmed alive at the time of completion or discontinuation of the survey. The endpoint will be censored on the day when patient's survival was last confirmed.
- Overall survival after the final dose of this drug in patients who underwent HSCT:
  - Overall survival: Defined as the months from the date of final dose of this drug to all-cause death.
  - Event: Death
  - Censoring: The patient is confirmed alive at the time of completion or discontinuation of the survey. The endpoint will be censored on the day when patient's survival was last confirmed.

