#### 8.1.4. Time-to-event data

For time-to-event data, the median, 1st quartile, and 3rd quartile will be determined using the Kaplan-Meier method. The rate at each time point will also be determined. To estimate CIs, log-log transformation will be used (this corresponds to specifying loglog under the conftype option in the proc lifetest statement of the SAS® lifetest procedure). In addition, Kaplan-Meier plots will be presented.

When time data are compared between subgroups using the Kaplan-Meier method, the hazard ratio of event occurrence and its 95% CI will be determined using the Cox proportional hazards model (ties handled by the Breslow method). In addition, the hazard ratio and its 95% CI will be presented graphically.

In the analysis of time data with competing risks, the cumulative incidence rate at each time point that takes into account competing risks will be determined (this corresponds to using the event code option in the time statement of the SAS® lifetime procedure). The standard error is to be estimated by the delta method. In addition, the time course of cumulative incidence will be graphically presented.

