#### 8.2.4.5. Subgroup analyses

Subgroup analyses for hematologic response and MRD will be performed by each of the factors defined in Section 5.4. In addition, hematological response rate ratio and MRD negative rate ratio (corresponds to risk ratio in the SAS) for different subgroups will be determined as per Section 8.1.3, and presented graphically. If, however, there is a category with less than 10 patients and after reconsideration it is considered difficult to determine the ratios for the category, it will not be determined for the each of the relevant category.

In addition, subgroup analyses of OS will also be performed for each of the factors defined in Section 5.4. Hazard ratios for the occurrence of events for different subgroups will be determined as per Section 8.1.4 and graphically presented. If, however, there is a category with less than 10 patients and after reconsideration it is considered difficult to determine the hazard ratio for the category, it will not be determined for the relevant category. The OS after the final dose of this drug in patients who underwent HSCT will also be analyzed in the same manner. Results of the analysis for the entire analysis set should be interpreted with caution, because the planned observation period for this survey differs for patients who did and did not undergo HSCT after the start of this drug (see Section 2.1). The above subgroup analyses of OS will also be performed by HSCT performed or not performed after the start of this drug.

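### OS is counted from drug start but split by a later HSCT, so the two curves are not comparable, and the SAP's caution does not cover this

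*SAP*

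**What the plan says.** - **Clock.** SAP 6.2 gives OS as "Defined as the months from the start of this drug to all-cause death".
- **Split.** SAP 8.2.4.4 runs OS for the entire set "and also by HSCT performed or not performed after the start of this drug". Rates are reported at Months 3, 6, 9 and 12 for the entire set and for non-recipients, and "at Months 3, 6, 9, 12, 18, and 24 for patients who underwent HSCT". Both groups therefore share the first four time points.
- **Caution.** Results for the entire set are to be read carefully, "because the planned observation period for this survey differs for patients who did and did not undergo HSCT after the start of this drug". Nothing is said about the two HSCT groups.
- **Method.** SAP 8.1.4 provides Kaplan-Meier estimates and a Cox model: "When time data are compared between subgroups using the Kaplan-Meier method, the hazard ratio of event occurrence and its 95% CI will be determined". No landmark, time-dependent covariate or delayed entry is mentioned.
- **Subgroups.** SAP 8.2.4.5 adds: "The above subgroup analyses of OS will also be performed by HSCT performed or not performed after the start of this drug".
- **Listed factors.** In SAP 5.4 the safety list contains the entry "HSCT after the start of this drug [not performed, performed", but the OS list contains only "HSCT before the start of this drug [not performed, performed". The OS list also contains best overall response and MRD, both known only after drug start.

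**The concern.** Membership of the HSCT groups is settled after time zero. Someone in the HSCT group cannot, by construction, have died before HSCT. Someone who was heading for HSCT and died first sits in the other group. Recipients are credited with guaranteed survival time and non-recipients absorb the early deaths, whatever HSCT does to survival.

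OS is one of the two main efficacy endpoints (Protocol 8.12.2.2), the final analysis supports the re-examination application (SAP 3), and results may be published (Protocol 11). Two curves with shared time points invite comparison. SAP 6.4 adds to this by naming HSCT status as a possible prognostic factor for OS without saying whether HSCT before or after drug start is meant.

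Best response and MRD raise the same issue. SAP 8.2.4.1 allows a first CR/CRi to be dated in any cycle or post-treatment, so a late responder must have lived long enough to respond.

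**Working it through.** **No plan figure to reproduce.** The documents contain no OS assumption. The only design figure, 80.4% power for VOD/SOS risk factors, does not bear on this point.

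**Assumed inputs (not in the documents).** HSCT has no effect; death is exponential with median 26, 35 or 52 weeks; a share p = 40-60% is intended for HSCT, unrelated to prognosis; HSCT falls uniformly in weeks 4-8, 4-12 or 8-28, if the patient is alive. SAP 8.2.2 leaves timing open, with categories from under 4 to 28 or more weeks. Follow-up is 52 weeks, or 52 weeks after HSCT (SAP 2.1).

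**Formula.** Let S(t) be true survival and q the probability that an intended patient lives to HSCT, averaged over the window. For t at or beyond the end of the window:
- recipients: S(t) / q
- non-recipients: (1 - p) S(t) / (1 - p q)

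**Worked case: median 35 weeks, p = 0.5, weeks 4-12.**
- Rate = ln 2 / 35 = 0.0198 per week.
- q = (exp(-4 × 0.0198) - exp(-12 × 0.0198)) / (8 × 0.0198) = 0.854.
- Non-recipient denominator = 1 - 0.5 × 0.854 = 0.573.
- Month 6 (week 26): S = 0.598. Recipients 0.598 / 0.854 = 70%; non-recipients 0.5 × 0.598 / 0.573 = 52%; truth 60%.
- Month 12 (week 52): S = 0.357. Recipients 42%; non-recipients 31%; truth 36%. With HSCT at weeks 8-28 the pair is 51% and 28%.

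**Ranges over the grid, no HSCT effect (recipients vs non-recipients).**
- Weeks 4-8 or 4-12: Month 3, 83-94% vs 55-80% (truth 71-84%); Month 6, about 58-79% vs 39-67% (truth 50-71%).
- Weeks 8-28: Month 3, 98-99% vs 54-77%; Month 6, 79-90% vs 32-62%.

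**If a hazard ratio were computed for the split.** Under no effect, the ever/never Cox value is 0.64-0.78 (weeks 4-8), 0.58-0.72 (4-12) or 0.37-0.49 (8-28). A second set of assumptions (lognormal HSCT times with medians of 2 to 4.5 months; median OS 5 to 12 months; 60% candidates) gave 0.34-0.61.

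**If HSCT has an effect.** With a true post-HSCT hazard ratio of 1.5, weeks 4-12 and half the patients intended, the ever/never value is about 0.89-0.99, so harm is masked.

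**Candidate remedies.**
- HSCT as a time-dependent covariate: 0.99-1.01 under no effect.
- Simon-Makuch survival to week 52 under no effect, 50% intended: 0.346 vs 0.344, truth 0.345 (median 26, weeks 4-12, from week 12); 0.621 vs 0.619, truth 0.620 (median 52, weeks 8-28, from week 16).
- Week-16 landmark: 0.99-1.01 under no effect. With HSCT at weeks 8-28, however, a true 0.5 becomes about 0.65 and a true 1.5 about 1.27, because later recipients count as untransplanted. The time-dependent model does not dilute in this way.
- Share lost to a landmark at week L is 1 - 2^(-L/median). For L = 16 this is 1 - 2^(-16/52) = 19% to 1 - 2^(-16/26) = 35%.

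**Best response.** For CR/CRi against assessed non-responders (assessed at weeks 3-8) with no effect of response, the hazard ratio is 0.87-0.89 if responses are dated at weeks 3-16 and 0.76-0.81 at weeks 3-24. It is 0.43-0.80 if patients who die before responding are kept as non-responders. A time-dependent covariate returns 0.99-1.01.

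**Subgroups within each HSCT group (8.2.4.5).** A factor with no effect on death and unrelated to HSCT gives 0.99-1.02. Among recipients, it gives 0.63-0.85 if HSCT timing differs by the factor (weeks 16-28 vs 4-12, or 12-24 vs 8-16). Among non-recipients, it gives 1.22-1.50 if HSCT uptake differs (60% vs 20%, or 70% vs 30%). Starting recipients at HSCT returns 0.99-1.02.

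**The case against.** The best defence is that 8.2.4.4 is descriptive stratification. The SAP gives the groups different time points, explains that their follow-up differs, and never says the split estimates an HSCT effect. SAP 4.1 makes all testing exploratory with no significance level. Survival after HSCT is already analysed from the right origin: SAP 6.1 and 8.2.3.3 start the clock at the first HSCT. All of this stands and limits the severity. It does not supply the missing warning, and the post-HSCT analysis has no untransplanted group and no OS hazard ratios.

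Three stronger readings are tempting but unsupported:
- **The SAP plans an OS hazard ratio for HSCT against no HSCT.** It does not list one. HSCT after drug start is in the safety list and absent from the OS list; such a ratio would arise only if the groups were compared under 8.1.4.
- **Readers will see a false benefit.** That depends on the true effect. If HSCT were harmful, the same bias could bring the hazard ratio close to 1.
- **The curves are wrong.** Each is a valid description of the patients in it. Only the comparison fails.

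It is also fair that the sizes are assumptions throughout, and that the larger response bias needs early deaths to be counted as non-responders. SAP 5.4 keeps separate categories for indeterminate or other and for not performed, which may prevent that. The within-group distortions need sizeable assumed differences in HSCT uptake or timing.

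**Conclusion.** The point holds. The HSCT split in 8.2.4.4 conditions on a later event, the two groups' Month 3 to 12 rates are not comparable, and the existing caution addresses a different problem. The direction of the bias follows from the definitions and favours recipients. Its size rests on assumed OS, HSCT share and HSCT timing, so only the ranges should be quoted: under no HSCT effect, Month-6 OS of 58-79% vs 39-67% for early HSCT and 79-90% vs 32-62% for later HSCT.

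The planned OS hazard ratios by best response and MRD share the mechanism. The modelled response bias is modest if only assessed patients are compared (about 0.76-0.89 with no true effect) and larger otherwise. The damage is to how exploratory results are read; no confirmatory conclusion is at stake. This is worth correcting before the results are reported.

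**What to change.** 1. **SAP 8.2.4.4.** Present survival by HSCT status with Simon-Makuch curves, and use HSCT as a time-dependent covariate for any hazard ratio. A landmark fixed in advance can be a secondary display. If the ever/never curves stay as description, state beside them that they do not compare HSCT with no HSCT.
2. **OS by best response and MRD (5.4, 8.2.4.5).** Use a time-dependent covariate or a landmark fixed in advance.
3. **SAP 8.2.4.5, HSCT-performed group.** Run the subgroup analyses from the date of first HSCT, the clock already used in 6.1 and 8.2.3.3.

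**Cost.** SAP wording and modest programming. The dates are already collected or used: HSCT (Protocol 8.8.5), earliest MRD negativity (8.8.11.2), death (8.8.12) and the CR/CRi assessment (SAP 8.2.4.1). A landmark drops early deaths and pulls a true HSCT effect toward the null when HSCT comes after it. No method here removes the selection of fitter patients for HSCT, and the report should say so.

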8.8. Variables

The following information obtained during the observation period in the investigation is defined as survey items.

Table 1. Schedule of Observation

Variables	Registration form	Booklet 1		Booklet 2
		Baseline	Treatment phase*	
Patient background	ID number	●	○	
	Gender	●	○	
	Birth month and year (age at the start of the investigation if it is not provided)	●	○	
	Experience of participation in this investigation	●	○	
	(Planned) start date of BESONSA treatment	●		
	Target disease of the investigation	●		
	Informed consent from the patient (BESONSA treatment)* ³	●		
	Informed consent from the patient (publication of the investigation results)* ⁴	●	○	
	Patient registration number at the site from which the patient is transferred	●	○	
	Name of the site from which the patient is transferred	●	○	
	Height and weight		●	
	Target disease		●	
	Date of confirming the initial onset		●	
	Chromosomal karyotype		●	
	Medical history		●	
Treatment and clinical status	Treatment history at baseline (remission induction chemotherapies and HSCT from the initial onset)		●	
	BESONSA treatment record		↔↔	
	Pregnancy status		↔↔	
	Clinical laboratory tests (hematology, hepatic function test, renal function test, electrocardiography, pancreatic function test, bone marrow test)		●	▲
	ECOG PS	●	▲	▲
	Treatment of the target disease after the start of BESONSA treatment (HSCT, HSCT donor information, drug therapy, non-drug therapy)		↔↔	↔↔
	Prophylactic treatment for reducing infusion reactions		↔↔	
	Prophylactic treatment for preventing and reducing tumour lysis syndrome		↔↔	
	Clinical evaluation (hematologic remission and MRD)		↔↔	

PFIZER CONFIDENTIAL

CT24-WI-JPN-GPSP01-RF09 8.0 Non-Interventional Study Protocol Template for Secondary Data Collection

Study 01-Nov-2023

Page 16 of 33

Adverse events	Any AEs			↔	
	VOD/SOS			↔	↔
Records of treatment end/discontinuation			●		
Records of investigation continuation/discontinuation			●		●
Confirmation of survival (including reasons for death)			↔		↔

*: From treatment initiation to Day 28 post-treatment

*2: From Day 29 post-treatment to Week 52 (patients who did not undergo HSCT before Week 52) or 52 weeks after HSCT (patients who underwent HSCT before Week 52)

*3: Informed consent for BESPONSA treatment should be obtained after adequately explaining the efficacy of and risks from BESPONSA to the patient.

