8.8.9. Records of investigation discontinuation

For patients who withdraw from the investigation during the observation period, enter the date of discontinuation. For the main reason for discontinuation, i.e., why the investigation cannot be continued, select one of the following options.

(Not making another visit, death, transfer to another hospital or department, or other)

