## **3. INTERIM AND FINAL ANALYSES**

In this study, interim analyses for periodic safety update reports will be performed periodically. Among analysis items defined in this SAP, only the analysis items necessary for periodic safety reports will be analyzed at the time of interim analysis. In addition, a final analysis to support the re-examination application will be performed. All analyses specified in this SAP will be performed at the time of the final analysis.

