**Timing of onset of VOD/SOS:** To analyze the timing of onset of VOD/SOS, summary statistics will be performed as per Section 8.1.1, for the following kinds of time.

- Time from the final dose of this drug: Time (weeks) from the final dose of this drug to the onset of VOD/SOS
- Time from HSCT: Time (weeks) from the first HSCT after the start of this drug to the onset of VOD/SOS. Only VOD/SOS events that occurred with presence of HSCT after the start of this drug will be included in this analysis (Similar limitation shall also apply to the analysis set).

Patients with VOD/SOS will be counted by each of the following timing factors. For each timing factor, data will also be summarized in a histogram (The longitudinal axis is frequency. The width of each onset period will depend on the actual duration of the period).

- Time from the final dose of this drug: < 2 weeks, ≥ 2 weeks to < 4 weeks, ≥ 4 weeks to < 8 weeks, ≥ 8 weeks to < 12 weeks, ≥ 12 weeks to < 16 weeks, ≥ 16 weeks
- Time from HSCT 1: < 2 weeks, ≥ 2 weeks to < 4 weeks, ≥ 4 weeks to < 6 weeks, ≥ 6 weeks to < 8 weeks, ≥ 8 weeks. This time is defined as the time starting from the first HSCT after the start of this drug.
- Time from HSCT 2: ≤ 3 weeks, > 3 weeks. This time is defined as the time starting from the first HSCT after the start of this drug.

Regarding the timing of onset of events described in "Timing of onset of adverse drug reactions" in Section 8.2.3.1, data will be analyzed with the following specifications.

- Analysis set: Patients who finished the survey (Patients who are recorded as discontinued in the "Record of continued/discontinued survey [treatment period]" in the case report form or patients for whom "Record of continued/discontinued survey [follow-up period]" in case report form is filled in. The latter means the survey is discontinued and completed for the patient.)
- Handling of patients who did not experience ADRs: If the survey had been discontinued for the patient, data shall be censored on the date of discontinuation based on the "Record of continued/discontinued survey" in the case report form; if the survey had been completed for the patient, data shall be censored on the last observation date defined in Section 7.
- Time points for rate estimation: Every 4 weeks from Week 4 to Week 52

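### Restricting overall survival to patients who finished the survey drops continuing patients without a usable follow-up record, although they could be censored; relative to censoring them, estimated survival can only be equal or lower

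*SAP*

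**What the plan says.** SAP 8.2.4.4 first says that OS uses the entire analysis set, then limits it to "patients in the EAS who finished the survey". There are two ways to qualify. One is "Patients who are recorded as discontinued in the 'Record of continued/discontinued survey [treatment period]' in the case report form". The other is a filled-in follow-up-period record, of which the SAP says: "The latter means the survey is discontinued and completed for the patient". OS after the final dose in transplanted patients carries the same condition.

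The other relevant provisions are:

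- **Discontinuation reasons (Protocol 8.8.9):** "Not making another visit, death, transfer to another hospital or department, or other". A death in the treatment period therefore qualifies by the first route.
- **Survival data (Protocol 8.8, Table 1):** the row "Confirmation of survival (including reasons for death" is marked for both the treatment phase and the follow-up phase.
- **Censoring (SAP 6.2):** "The endpoint will be censored on the day when patient's survival was last confirmed". The same bullet describes censored patients as those confirmed alive when the survey was completed or discontinued.
- **Missing dates (SAP 7):** if the survival confirmation date is missing, the last observation date replaces it. Case report form entries without a valid contract-physician signature are treated as missing.
- **Analysis sets (SAP 5.1, 5.2):** criterion a removes only patients with no case report form at all. No criterion names a missing follow-up record.
- **Same restriction elsewhere:** mortality after HSCT (SAP 8.2.3.3), and VOD/SOS onset (SAP 8.2.3.1), where the wording is "Analysis set: Patients who finished the survey".

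**The concern.** Entry to the OS analysis depends on what happens after time zero. Take two patients who are both alive 28 days after the final dose and recorded as continuing. If the follow-up record of one is not returned, or is set to missing for lack of a signature, that patient disappears from the analysis, together with the time already observed. A patient who dies in the treatment period can never disappear in this way. A patient who leaves the survey alive during treatment also stays in and is censored. The rule thus keeps early deaths and early departures, and removes people with longer observed survival.

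Protocol 8.12.2.2 names OS as a main efficacy endpoint, and SAP 4.1 treats p-values as descriptive. The survival estimates are therefore what readers will use. SAP 8.2.4.4 cautions about unequal observation periods with and without HSCT, but not about this selection.

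**Working it through.** **The plan's own figure.** The only design calculation is the power for VOD/SOS risk factors (Protocol 8.10.2). An overall incidence of 12.3% with relative risk 3 and 1:1 groups gives 6.15% and 18.45%. With 88 per group and two-sided 0.1, power is Φ{[0.123 − 1.645·√(2·0.123·0.877/88)] / √[(0.1845·0.8155 + 0.0615·0.9385)/88]} = 80.4%, as stated. It has no bearing on OS. The documents give no OS rate, event count or follow-up return rate, so the sizes below rest on assumptions.

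**Who is dropped.**

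| Status at end of treatment period | Follow-up record | In the OS analysis? |
|---|---|---|
| Died | not needed | yes, event |
| Left the survey alive | not needed | yes, censored |
| Continuing | usable | yes |
| Continuing | absent or unusable | **no** |

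**Direction.** At a death time with d deaths and n at risk, the Kaplan-Meier factor is 1 − d/n. Suppose r of those at risk belong to the dropped group. They carry no usable record of death, so d is unchanged and the factor becomes 1 − d/(n − r), which is equal or lower. Every factor moves the same way, so the restricted curve cannot lie above the curve that censors these patients.

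**Size, closed form.** Let p be the share who die in the treatment phase, m the share of treatment-phase survivors without a follow-up record, and t0 a common end of the treatment phase, with no earlier censoring. The restricted set keeps 1 − (1 − p)m of the patients and (1 − p)(1 − m) as survivors, so

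S_restricted(t0) = (1 − p)(1 − m) / [1 − (1 − p)m], against 1 − p.

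For p = 20% and m = 10%: 0.72/0.92 = 78.3% against 80.0%. In 176 patients this removes 176 × 0.8 × 0.1 ≈ 14.

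| p | All included | m = 5% | m = 10% | m = 20% |
|---|---|---|---|---|
| 10% | 90.0% | 89.5% | 89.0% | 87.8% |
| 20% | 80.0% | 79.2% | 78.3% | 76.2% |
| 30% | 70.0% | 68.9% | 67.7% | 65.1% |

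**Size, simulation.** Assumptions: N = 176, exponential survival, 1 to 3 cycles, and records missing unrelated to later survival. The entries are restricted minus censored-inclusive, in percentage points.

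| m | Month 3 (12-month OS 45%) | Month 12 (12-month OS 45%) | Month 3 (12-month OS 30% to 60%) |
|---|---|---|---|
| 5% | −0.6 | −0.3 | −0.7 to −0.4 |
| 10% | −1.2 | −0.7 | −1.5 to −0.8 |
| 20% | −2.5 | −1.4 | −3.3 to −1.8 |

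No simulated data set put the restricted curve above the other. A second simulation (20,000 patients, 12-month OS 40%, 1 to 5 cycles) gave 78.4% against 79.7% at Month 3 for m = 10%, and 76.2% against 79.0% for m = 20%. This is the source of the range 0.6 to 2.8 points for 12-month OS of 40-45%. At m = 0 the difference is zero.

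**Informative missingness.** With 12-month OS 45% before adjustment and m = 20%, let patients without a record die at twice the hazard after the treatment phase.

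| | Truth | Censored-inclusive | Restricted |
|---|---|---|---|
| Month 3 | 80.9% | 81.8% | 79.2% |
| Month 12 | 40.5% | 44.7% | 43.2% |

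Here the restricted estimate is too low at Month 3 and too high at Month 12, and plain censoring is biased upward at both.

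**The case against.** **The group may be empty at the final analysis.** This stands. The last eligible start is 30 April 2020 (Protocol 8.4). The longest observation is 52 weeks to HSCT plus 52 weeks after it, ending about late April 2022, some two years before the database release planned for May 2024 (Protocol 5). Only records not returned, unsigned or set to missing remain. Even at m = 10% the shift is well inside the sampling error: with S = 0.80 and N = 176, the 95% half-width is about 1.96·√(0.8·0.2/176) = 5.9 points.

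**SAP 6.2 supports the restriction.** This stands in part. Its censoring condition refers to patients confirmed alive at completion or discontinuation, which a continuing patient without a follow-up record does not literally meet. Section 7 still supplies a usable date, so the wording needs aligning. The patient need not be dropped.

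**Stronger readings that the documents do not support.**

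- *All patients alive at the end of treatment are dropped.* Only continuing patients without a usable follow-up record are.
- *True survival is underestimated.* The direction is certain only relative to the censored-inclusive analysis. Dropped patients are known to be alive only to about Day 28 after the final dose, and some may have died later.
- *Interim results are badly distorted.* The SAP says "interim analyses for periodic safety update reports will be performed periodically", but limits them to items needed for those reports. It does not say that OS is one.
- *VOD/SOS onset is biased in the same direction.* VOD/SOS does not by itself end the survey, so a case in the treatment phase without a follow-up record is removed together with its event.

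**Conclusion.** The point holds in a limited form. The finished-survey condition selects on a later event, and the OS analysis does not need it. If every continuing patient has a usable follow-up record, it changes nothing. If some do not, it removes patients who could be censored, and the Kaplan-Meier estimate is equal or lower than with them included.

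Under an assumed 5-20% of treatment-phase survivors without a follow-up record, the Month-3 loss is roughly 0.6-2.8 points for 12-month OS of 40-45%, and it is smaller at Month 12. The true share is not in the documents and may be near zero.

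Two conditions apply. The dropped patients must have no usable record of death, and they must be in the EAS. SAP 5.2 criterion h is worded generally and could be applied to some of them, but 8.2.4.4 itself presupposes EAS patients who have not finished. No direction is claimed against true survival or for VOD/SOS onset.

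**What to change.** - **SAP 8.2.4.4:** analyse OS in all EAS patients, and OS after the final dose in all EAS patients who underwent HSCT after the start of the drug. Censor those without a follow-up record at the last confirmed survival date, or at the Section 7 last observation date if that is missing.
- **SAP 6.2:** align the censoring wording, so that it also covers patients with neither a completion nor a discontinuation record.
- **Reporting:** state how many EAS patients lack a usable follow-up record. Keep the finished-survey set as a sensitivity analysis. If the number is not trivial, say that censoring assumes their later survival is like that of the others.
- **SAP 8.2.3.3, mortality after HSCT:** make the same change, with the matching censoring wording in 6.1.
- **SAP 8.2.3.1, VOD/SOS onset:** include all SAS patients. Censor event-free patients without a follow-up record at the last date on which VOD/SOS status was observed, for example the end of the treatment period. A survival contact alone does not establish VOD/SOS status.

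The cost is SAP wording, a few more censored records and a rerun of the affected tables. No new data are needed. SAP version 6.0 (2 September 2024) postdates the planned database release, so the change should be documented as made after that point. Keeping the finished-survey results alongside makes its effect visible.
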